7. STUDY EQUIPMENT

7.1 Digital micrometer to determine hair diameter will be used.

7.2 pH meter to measure the pH of the solutions will be used.

8. DATA DISCLOSURE AND SUBJECT CONFIDENTIALITY

The information that will be generated from this research project will be kept confidential. Information about subjects that will be collected during the research will be put away, and no-one but the investigations will be able to see it. Any info about subjects will have a number on it instead of their name. Only the researchers will know what their number is, and we will lock that information up with a lock and key. Data generated as a result of this study will not be shared with or given to anyone except the food and drug administration and Tabriz University of medical sciences Ethics Committee (EC), upon their request. The information from this study, if published in scientific journals or presented at scientific meetings, we will not be sharing the identity of the subjects in the research.

9. EFFICACY ASSESSMENT

Efficacy Assessment will be done based on the primary and secondary outcome measures mentioned above.

10. SAFETY ASSESSMENT

Any procedure has potential risks. According to the herbal origin, the topical herbal solution does not hold any chance of dangerous reactions or systematic disease. The threat from the use of topical solutions may include scalp itching, scalp dryness, and headache. The procedures used in this study may cause all, some, or none of the risks and side effects listed. Each study participant will be informed about the occurrence of these adverse events, and phone numbers will be given for answering any questions. Telephone contact with the investigator will be available 24 hours per day, seven days per week. Treatment for adverse events will be per standard of care from a dermatologist in the Department of Dermatology.

11. STATISTICAL ANALYSIS PLAN (SAP)

The statistical analysis will be performed using SPSS software 25 (SPSS Inc., Chicago, IL, USA). The normalcy of continuous data will be checked using the Kolmogorov-Smirnov Test. Mean (SD) will be calculated for all normally distributed continuous variables, e.g., age, duration of disease, hair diameter, etc. The unpaired (independent) t-test and paired t-test will be applied to compare the mean of hair diameter between two study groups and within

groups, respectively. For differences between self-assessment questionnaires, the Mann-Whitney test will be performed. At or before the time of the Week 0 administration, subject demographics, hair diameter, and duration of AGA will be summarized. All statistical tests will be two-side and will perform at a significance level of p -value < 0.05 .

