2. STUDY DESIGN

This study will be done on male patients with androgenic hair loss. The patients will be selected by volunteers attending the Dermatology department of Sina Hospital and eligible individuals will be selected among them. The participants will be randomly allocated (using random number tables) to two groups; the first group will receive a 5% minoxidil topical solution, and the second group will receive a 5% minoxidil topical solution plus the topical herbal solution for 36 weeks. The hair thickness will be measured to determine efficacy at baseline, 12, 24, and 36 weeks. The patient's questionnaire self-evaluation and side effects will also be evaluated.

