5.2 Treatment Visit

- In addition to oral explanations, participants will be given written instructions on how to use solutions and storage conditions.
- Subjects will not be permitted to apply their usual hair cosmetics products and will be requested not to alter their usual routine hair care during the study period.
- Subjects will be instructed to avoid the use of any prescribed and/or nonprescription therapeutic agents for preventing hair loss or hair growth during the study period.
- Baseline hair thickness will be taken, and every three months, it will be repeated. For reproducibility, the target location on the scalp, where the hair thickness will be measured over time, consist of Intersecting three distances from the fixed anatomical locations.

Treatment randomization

Before the study begins, a random number table will be generated (in 1:1 ratio) for each study participant according to the subject number. The number will indicate whether treatment or control will be taken on the study groups. “0” represents a 5% minoxidil topical solution whereas “1” represents a 5% minoxidil topical solution plus the topical herbal solution.

Blinding

Dermatologist and the randomized subjects will be blinded to the subject’s allocation. It is necessary to use blinded treatment in order to reduce potential bias during data collection and evaluation of study outcomes.

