6. DATA COLLECTION AND REPORTING

6.1 Primary Outcome Measures

Hair thickness via a digital micrometer will record for each subject by a blinded investigator at the treatment visit (before treatment) and during the three months, six months, and 9-month follow-up visits.

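### The only between-group test of hair diameter is an unadjusted t-test; the baseline value taken in every subject should enter it as a covariate

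*Combined protocol and SAP*

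**What the plan says.** Section 6.1 makes hair thickness, measured by digital micrometer, the primary outcome. It is recorded by a blinded investigator "at the treatment visit (before treatment) and during the three months, six months, and 9-month follow-up visits". Section 2 gives the same schedule in weeks: "The hair thickness will be measured to determine efficacy at baseline, 12, 24, and 36 weeks". Section 5.2 repeats it ("Baseline hair thickness will be taken, and every three months, it will be repeated") and defines "the target location on the scalp, where the hair thickness will be measured over time" by distances from fixed anatomical points, so that the site can be found again. Allocation is 1:1 from a random number table.

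Section 11 contains the whole analysis of this outcome: "The unpaired (independent) t-test and paired t-test will be applied to compare the mean of hair diameter between two study groups and within" groups, in that order. The unpaired test is therefore the between-group test and the paired test is the within-group one. For Week 0, "subject demographics, hair diameter, and duration of AGA will be summarized". On testing: "All statistical tests will be two-side and will perform at a significance level of p -value < 0.05".

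No covariate, ANCOVA, regression, mixed model or between-group test of change appears. Section 9 refers back to the outcome measures and adds no method. Baseline diameter is thus used for the Week 0 summary and, by implication, in the paired tests.

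**The concern.** The trial measures baseline diameter at a relocatable site in each man and then leaves it out of the comparison that answers its question. On the literal reading, the unpaired test compares raw diameters. All stable variation between men in hair diameter then stays in the error term, so the confidence interval is wider and power lower than the collected data allow.

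The wording also leaves the compared quantity open. An analyst could use follow-up values or changes from baseline, and could choose after seeing the data. The choice matters: the change score is more precise than the raw value when r is above 0.5 and less precise when it is below. Neither version adjusts for baseline by regression.

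**Working it through.** **Inputs from the documents.** Two parallel groups, 1:1 (Sections 2 and 5.2); two-sided 0.05 (Section 11); baseline and three follow-up measurements (Sections 2 and 6.1). The plan states no power or sample-size figure, so there is nothing to reproduce.

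**Assumptions.** Correlation r between baseline and follow-up diameter from 0.2 to 0.9; equal SD at both times; a true difference of 0.5 SD; 30 or 63 per arm for illustration.

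**Step 1: variance of the between-group estimate, relative to the raw t-test (= 1).**

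- ANCOVA: 1 − r²
- Change score: 2(1 − r)

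**Step 2: power.** Noncentral t with noncentrality (0.5/√variance ratio) × √(n/2), on 2n − 2 degrees of freedom for the raw and change tests and 2n − 3 for ANCOVA. Example at n = 30 and r = 0.5:

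- Raw: 0.5 × √15 = 1.936 on 58 df, power 48%.
- ANCOVA: variance ratio 1 − 0.25 = 0.75; 0.5/√0.75 = 0.577; 0.577 × √15 = 2.236 on 57 df, power 59%.

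| r | Variance, ANCOVA | Variance, change | CI narrowing, ANCOVA vs raw, 1 − √(1 − r²) | Power, 30/arm: ANCOVA (raw 48%) | Power, 30/arm: change | Power, 63/arm: ANCOVA (raw 80%) |
|---|---|---|---|---|---|---|
| 0.2 | 0.96 | 1.60 | 2% | 49% | 33% | 81% |
| 0.3 | 0.91 | 1.40 | 5% | 51% | 36% | 83% |
| 0.5 | 0.75 | 1.00 | 13% | 59% | 48% | 90% |
| 0.7 | 0.51 | 0.60 | 29% | 76% | 69% | 97% |
| 0.8 | 0.36 | 0.40 | 40% | 89% | 85% | 99.6% |
| 0.9 | 0.19 | 0.20 | 56% | 99% | 99% | >99.9% |

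**Step 3: small-sample cost of estimating the slope.** With N subjects in total, the ANCOVA variance is multiplied by about 1 + 1/(N − 4). At 30 per arm this is 1 + 1/56 = 1.018, which lowers the ANCOVA powers above by at most about 0.8 points. ANCOVA then beats the raw test once r exceeds about 0.24 at 10 per arm, 0.16 at 20 and 0.13 at 30.

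**Step 4: validity.** In simulation (20,000 trials per setting, 12 to 50 per arm, r = 0.3 to 0.85), type I error was 4.6–5.2% for the raw t-test and 4.6–5.4% for ANCOVA. With the true difference set so that the raw test had nominal 80% power, simulated power at 30 per arm was 78% raw against 82% ANCOVA at r = 0.3, 78% against 88% at r = 0.5, and 79% against 97% at r = 0.7.

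**Step 5: the same loss seen in a single trial.** If the groups differ at baseline by g SD, the expected raw estimate moves by r × g and the change-score estimate by (r − 1) × g. The chance of a gap above 0.3 SD in either direction is 2[1 − Φ(0.3/√(2/n))]:

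- n = 30: 0.3/0.258 = 1.16, giving 25%
- n = 63: 0.3/0.178 = 1.68, giving 9%
- n = 100: 0.3/0.141 = 2.12, giving 3%

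A gap of 0.3 SD at r = 0.7 moves the raw estimate by 0.7 × 0.3 = 0.21 SD and the change estimate by −0.3 × 0.3 = −0.09 SD. This is not a second problem: chance imbalance is already part of the unadjusted variance in Step 1.

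**The case against.** A two-sample t-test is a legitimate analysis of a randomised two-arm trial, and nothing in Section 11 contradicts the design. This stands: the point concerns efficiency and definition, not error.

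The size of the gain is unknown. The documents give no r, and although the scalp site is fixed, they do not say that the same hairs, or how many, are measured. A high r cannot be presumed. This stands too, and it is why a range is shown that starts at almost nothing.

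The large gains over the raw test need r of about 0.7 or more, and there the change score is nearly as good as ANCOVA (0.60 against 0.51 at r = 0.7; 0.20 against 0.19 at r = 0.9). If change was intended, the benefit of ANCOVA lies mainly at low r. This is correct, but it does not favour the present text, which names neither quantity. Apart from the small-sample cost, ANCOVA is at least as precise as both across the range of r, so adopting it removes the need to know which was meant.

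In a very small trial ANCOVA can lose slightly. At 10 per arm and r = 0.2, power for 0.5 SD is 18.2% against 18.5% for the raw test. That is a trivial price.

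**Conclusion.** The concern holds. On either reading of Section 11, baseline diameter is not a covariate in the between-group test of the primary outcome, and no other section supplies an adjusted analysis. The planned test is valid under randomisation; what is lost is precision, and what is missing is a definition of the compared quantity.

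Confidence is high that baseline is omitted, but not in any one figure for the loss. Against the raw t-test, the variance reduction runs from 4% at r = 0.2 to 81% at r = 0.9. Against a change-score test it runs from 40% (1 − 0.96/1.60) to 5% (1 − 0.19/0.20). These figures rest on the assumed r and on equal SDs; the powers also rest on the assumed arm sizes and the 0.5 SD difference. The plan should be changed because the improvement is nearly free, not because the present test would mislead.

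**What to change.** Replace the unpaired t-test sentence in Section 11 with wording such as:

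> The between-group analysis of hair diameter will be an ANCOVA of 36-week hair diameter with treatment group and baseline hair diameter as terms, reporting the adjusted mean difference with its 95% confidence interval. The unadjusted t-test on 36-week diameter will be a sensitivity analysis.

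Week 36 is used because Section 2 gives it as the end of treatment. Sections 6.1 and 11 name no primary visit, so that choice has to be written down as well. It is a separate gap, which ANCOVA alone does not close.

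A repeated-measures mixed model over the three follow-up visits with baseline as covariate is an acceptable alternative. It is not equivalent: it uses the earlier visits and handles missing data under different assumptions.

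The cost is a change of SAP wording, one degree of freedom and the small slope-estimation penalty. No new data, visits or subjects are needed, and SPSS 25, the stated software, fits the model. The change should be made before unblinding, so that the adjustment cannot be seen as chosen from the results.

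### Sections 9 and 11 do not say that only the between-arm test decides efficacy, although the within-arm paired test cannot separate the herbal solution from minoxidil

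*Combined protocol and SAP*

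**What the plan says.** Section 11 names both tests together: "The unpaired (independent) t-test and paired t-test will be applied to compare the mean of hair diameter between two study groups and within" each arm, and it assigns them in that order. The unpaired test therefore compares the arms and the paired test looks within each arm. That the paired test sets follow-up against baseline is implied, not written. The error level is common to everything: "All statistical tests will be two-side and will perform at a significance level of p -value < 0.05". No test is ranked above another, and the paired test is not called descriptive.

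Section 9 reads: "Efficacy Assessment will be done based on the primary and secondary outcome measures mentioned above". It points to outcomes and names no test, contrast or visit. Section 6.1 defines the primary outcome only as hair thickness recorded before treatment and at three, six and nine months.

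On treatment, Section 2 says that "the second group will receive a 5% minoxidil topical solution plus the topical herbal solution for 36 weeks"; the other arm has minoxidil alone. The allocation codes in Section 5.2 are likewise only two, and both contain minoxidil. Section 3 presents minoxidil as an approved therapy for this condition. Section 1 states the objective in two parts: the effect of the herbal solution, and a comparison with minoxidil.

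**The concern.** The scientific question is what the herbal solution adds. In the herbal arm, change from baseline mixes any herbal effect with the response to minoxidil and with anything else that shifts over 36 weeks. No untreated arm, vehicle arm or run-in lets these be separated within one arm. Only the randomised contrast cancels what the two arms share.

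The two-part objective makes a misreading easy. The paired test could be matched to the effect of the herbal solution, and the unpaired test to the comparison with minoxidil. That pairing is an inference, but nothing in Sections 9 or 11 rules it out. At stake is whether a within-arm p-value below 0.05, which minoxidil alone could produce, may be reported as evidence for the herbal solution.

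**Working it through.** There is no figure of the plan's own to reproduce. The documents as supplied give no sample size, power, standard deviation or expected effect. The only numerical input is the two-sided level of 0.05. The rest is assumed, to show a range.

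**Inputs**
- From the documents: level 0.05 two-sided (Section 11); minoxidil in both arms and follow-up at weeks 12, 24 and 36 (Section 2); 1:1 allocation (Section 5.2).
- Assumed: n per arm of 10 to 50; normal data; zero herbal effect; standardised mean change dz (mean change divided by SD of change) of 0 to 0.8, equal in both arms.

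**Step 1. Paired test in the herbal arm, one visit.** The test is significant when |T| exceeds the 0.975 quantile of t with n − 1 degrees of freedom. T is noncentral t with noncentrality dz × √n. For n = 20, √20 = 4.472, so the noncentrality is 1.34, 2.24 and 3.58 for dz = 0.3, 0.5 and 0.8. The probability of significance with no herbal effect is:

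| n per arm | dz = 0 | dz = 0.3 | dz = 0.5 | dz = 0.8 |
|---|---|---|---|---|
| 10 | 0.05 | 0.14 | 0.29 | 0.62 |
| 20 | 0.05 | 0.25 | 0.57 | 0.92 |
| 30 | 0.05 | 0.36 | 0.75 | 0.99 |
| 50 | 0.05 | 0.55 | 0.93 | >0.99 |

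The first column matters: with no shared change over time, the paired test keeps its 5% level. The excess comes entirely from shared change.

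**Step 2. Between-arm test at week 36.** This was simulated with 20,000 trials per setting for n = 20, 30 and 50 and dz = 0, 0.3, 0.5 and 0.8. Baseline SD was 1 and the correlation between visits 0.7, so the SD of change is √(2 × (1 − 0.7)) = 0.775. The same mean shift, dz × 0.775, was given to both arms at every follow-up visit. The unpaired t-test on week-36 diameter was significant in 0.048 to 0.052 of trials, whatever the minoxidil response. Simulation error is about √(0.05 × 0.95 / 20,000) = 0.0015, so this agrees with 0.05.

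**Step 3. Why one visit must be named.** In the same simulation, if a significant result at any of the three follow-up visits may count without adjustment, the between-arm rate rises to about 0.11 (0.106 to 0.112). The herbal arm's paired test then reaches 0.47, 0.81 and 0.99 at n = 20 for dz = 0.3, 0.5 and 0.8. Restricting efficacy to the between-arm test without fixing the visit would leave about twice the nominal error.

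**The case against.** The strongest reply is that the right test is already there. The unpaired comparison comes first in the Section 11 sentence, the trial is randomised 1:1, and the objective includes a comparison with minoxidil. Giving minoxidil to both arms is an ordinary add-on design, in which the between-arm difference isolates the herbal increment. This stands. Shared minoxidil is a problem for the paired test only, and the absence of an untreated arm is not a flaw of the design.

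A reader might infer more than the text supports, in three ways:
- That Section 9 counts the paired test as efficacy. It does not; it refers to outcome measures and is silent on tests. The fair statement is that it does not exclude the paired test.
- That the plan will declare the herbal arm a success on a within-arm result. There is no success rule of any kind.
- That the plan compares significance in one arm with non-significance in the other. No such comparison is written. If someone made it, the chance with no herbal effect would be p(1 − p), where p is the probability in Step 1. At n = 20 and dz = 0.5 this is 0.565 × 0.435 = 0.25, the largest value it can take to two decimals. That warns about reporting; it is not an error rate of this plan.

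Other sources of within-arm change carry little weight. Season is not mentioned in the documents. The natural course of a miniaturising condition would be expected to thin hair, and so to work against a favourable change. Section 5.2 does say that "Subjects will not be permitted to apply their usual hair cosmetics products", but the same sentence also asks men to keep their routine hair care unchanged. The argument therefore rests mainly on minoxidil.

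Finally, the probabilities depend on assumed n and dz, which the documents do not give. This is also true. The direction needs only some shared improvement over time; the size cannot be fixed from the documents.

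**Conclusion.** The point holds as a gap in specification. Section 11 applies the within-arm and between-arm tests to the primary outcome at the same level, and neither it nor Section 9 reserves the efficacy conclusion for the randomised contrast. If minoxidil works, the herbal arm's paired test is likely to be significant without any herbal effect. Illustratively this probability is 0.25 to 0.92 at an assumed 20 men per arm and dz of 0.3 to 0.8, and 0.05 if nothing changes over time. The between-arm test at one fixed visit stays at about 0.05. These figures assume normal data and an equal minoxidil response in both arms.

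It should be fixed, as a cheap improvement. It does not rank as a must-fix, because the valid between-arm test is already planned and the documents contain no rule that turns a within-arm result into a claim of efficacy.

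**What to change.** In Sections 9 and 11, state that efficacy of the herbal solution is judged only on the randomised between-arm difference in hair diameter at one named visit, for example week 36, preferably adjusted for baseline diameter. Add that within-arm changes are reported descriptively, as mean change with a 95% confidence interval for each arm and visit, and are not evidence of a herbal effect.

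The cost is about two sentences of wording, settled before the data are analysed. No extra participants, visits or measurements are needed. The sponsor gives up within-arm p-values as evidence of efficacy.

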13. ETHICAL CONSIDERATIONS

13.1 Human Subjects Protection

The EC must be notified of the completion of the study. After study completion or termination, a final report must be provided to the EC to close the study. The investigator must maintain an accurate and complete record of all submissions made to the EC, including a list of all reports and documents submitted. Adverse events are reported to the FDA. This clinical trial study will conduct in accordance to the Declaration of Helsinki.

13.2 Consent Form

Before study entry, written informed consent must be given from each subject. A copy of the subject's signed consent form must be retained in the study file.

13.3 Protocol Amendments

All changes must be submitted to the EC Protocol modifications that impact subject safety, or the EC must approve the validity of the study before initiation.

13.5 Use of Information and Publication

The Principal Investigator or sub-investigator may publish the results of this study in conjunction with appropriate scientific and medical personnel.
